#### **11.1.5. Anticipated Serious Adverse Events Associated with PSC**

There are a number of events which are commonly associated with PSC and for the Sponsor's regulatory reporting purposes, these events are considered to be 'Expected' in this patient population and are listed in the IB.

The Investigator remains responsible for reporting to the Sponsor all SAEs including the events identified here:

- GI and hepatic malignancies including CCA, pancreatic cancer, colorectal cancer
- Ascites
- Cholecystitis
- Cholangitis (including bacterial cholangitis)
- Pancreatitis
- IBD and IBD flare (including UC and CD)
- Bile duct strictures (dominant or otherwise)
- Steatorrhea

- Vitamin deficiency
- Osteoporosis/osteopenia
- Fractures
- Variceal bleeding
- Cirrhosis
- Worsening PSC
- Any of the above that result in Death

#### **11.1.6. Additional Investigator Responsibilities for SAEs**

The safety data recorded in the CRF represent the official record of all AEs and SAEs reported in the trial. The Investigator should comply with requests by the Medical Monitor or other Sponsor personnel to record the SAE on the subject's AE CRF. Other supporting documents such as radiology reports, hospital discharge summaries, and autopsy reports should also be provided, when appropriate. Additionally, upon request by the Sponsor, the Investigator should provide input into the SAE narrative and provide timely information to ensure prompt follow-up and closure of the SAE report.

The Investigator and supporting personnel responsible for subject care should discuss with the Medical Monitor any need for supplemental investigations of SAEs. The results of these additional assessments must be reported to the Medical Monitor.

#### **11.1.7. Notification of Post-Trial SAEs**

If an Investigator becomes aware of an SAE that may be attributable to the investigational product at any time after the end of the trial, the Sponsor should be notified immediately (ie, within 24 hours).

All SAEs that occur within 30 days following the cessation of investigational product, whether or not they are related to the trial, must be reported to the Sponsor within 24 hours by following the instructions provided in [Section 11.1.4.2](#).

#### **11.1.8. Follow-Up of AEs and SAEs**

All AEs must be followed during the course of the trial until the AE resolves, is no longer of clinical concern, has stabilized or is otherwise explained, or the subject is lost to follow up.

AEs ongoing at the final visit that are deemed to be 'possibly, probably, or definitely' related or of other clinical significance must be followed for as long as necessary to adequately evaluate the safety of the subject or until the event stabilizes, resolves, or is no longer of clinical concern. If resolved, a resolution date for the AE should be documented on the CRF. The Investigator must ensure that follow-up includes any supplemental investigations indicated to elucidate the nature and/or causality of the AE. This may include additional laboratory tests or investigations, or consultation with other healthcare professionals, as considered clinically appropriate by the Investigator.

All subjects showing possible drug-induced liver injury should be followed until all abnormalities return to normal or to the baseline state. Drug-induced liver injury may develop or progress even after the causative drug has been stopped. Results should be recorded in the CRF. Note that longer follow-up can sometimes reveal an off-drug repetition of what had appeared to be drug-induced liver injury, indicating that liver injury was related to underlying liver disease.

### **11.1.9. Pregnancy and Follow-Up**

Pregnancies are not considered SAEs in and of themselves; however if a female trial participant becomes pregnant while she is enrolled in the clinical trial investigational product must be stopped immediately. The Sponsor must be notified within 24 hours of the Investigator's awareness of the pregnancy by completing the Pregnancy Notification Form and faxing or emailing to the Sponsor at [name] or [[contact]](mailto:[contact]).

The subject must be followed by the Investigator through pregnancy outcome. The Investigator should notify the Sponsor of the outcome of the pregnancy by completing the Pregnancy Outcome Form and faxing or emailing to the Sponsor. The mother (and infant) will be followed as considered appropriate by the Investigator and the Medical Monitor.

The Investigator must contact the Intercept Medical Monitor and discuss, in advance, any subject whose pregnancy is early terminated and would like to continue to participate in the trial. A minimum requirement for allowing the subject to restart dosing is documentation of a negative serum  $\beta$ -hCG test. However, this is not in and of itself a guarantee for being allowed to continue in the study.

## **11.2. Other Safety Parameters**

### **11.2.1. Medical History/Demographics**

A complete medical history will be obtained from the subject at screening. Demographic characteristics (age, gender, race, ethnicity, etc) will be recorded, as will any historical or on study data on colonoscopies (mucosal and histological) within the last 3 years and prior and on study liver biopsies, hepatic imaging, etc. Reports should be available in source data.

### **11.2.2. Physical Examination**

To assess the Subject for clinical findings, the Investigator or designee will perform a physical examination at the time points specified in the Schedule of Trial Procedures ([Table 1](#) and [Table 2](#)). If clinically significant abnormalities are observed before administration of the first dose of investigational product on Day 1, they should be reported as adverse events. If clinically significant abnormalities are observed after the first administration of investigational product on Day 1, the Investigator should assess and decide if they are new adverse events and report them accordingly. The physical examination should include the following at a minimum:

- General appearance
- Height (Screening visit only)
- Weight
- Skin

- Head, eyes, ears, nose and throat (HEENT)
- Neck
- Lymph nodes
- Chest/Respiratory system
- Cardiovascular system
- Abdominal region
- Extremities
- Musculoskeletal system
- Mental status
- Neurological system.

### **11.2.3. Vital Signs**

Vital signs will be assessed at indicated visits: oral temperature, sitting heart rate, respiratory rate and sitting blood pressure (BP). When taking heart rate, respiratory rate and BP readings, subjects should be seated quietly for a minimum of 3 minutes before the readings are taken.

### **11.2.4. Electrocardiogram**

Standard 12-lead ECGs will be collected. The Investigator or designee will review the 12-lead ECG and findings will be recorded in the CRF as normal, abnormal but not clinically significant, or abnormal and clinically significant. Any clinically significant abnormalities on ECGs recorded after Screening will also be documented as AEs and entered on the AE page of the CRF.

Investigative sites must retain a copy of all 12-lead ECGs evaluated by the Investigator or designee. These ECGs must be clearly labeled with the Subject ID number, date and time.

### **11.2.5. Laboratory Assessments**

All laboratory tests will be analyzed by a Central Laboratory (except urine or serum pregnancy tests). Blood and urine samples will be collected and analyzed or tested, according to the SOP of the testing facility and all samples will be collected while the subject is fasting. Full instructions concerning the number, volume, and type of samples to be collected at each visit will be detailed in the trial-specific laboratory manual. The manual will also include details of sample collection methods, labelling, and shipping information.

Fasting (8 hours) blood samples are required for lipid, glucose (serum chemistry), and bile acid analyses. For consistency, subjects will be instructed to attend each of their onsite visits (except Screening) in a fasted state and subjects should remain fasted until their blood samples have been collected. At each visit the Investigator or designee will verify whether the subject has fasted for at least 8 hours and record fasting status in the source and CRF. If the subject reports having

eaten (water is permitted) within 8 hours, this should be documented accordingly in the source and CRF and remind the subject that fasting is required prior to all trial visits.

- Hematology and Coagulation (hemoglobin, hematocrit, white blood cell [WBC] count with differential, platelets, red blood cell [RBC] count, INR, prothrombin time, partial thromboplastin time)
- Serum chemistry including albumin, blood urea nitrogen (BUN), creatinine, direct (conjugated) bilirubin, indirect (unconjugated) bilirubin, total bilirubin, AST, ALT, ALP, GGT, electrolytes [calcium, chloride, potassium, sodium, magnesium], glucose, total protein, and blood lipids (total cholesterol, low density lipoprotein [LDL], HDL and very low density lipoprotein (VLDL) fractions and triglycerides [TG])
- Apolipoprotein and NMR lipoprotein panel: ApoA1, ApoB, ApoE, HDL, LDL, triglycerides, VLDL. HDL, LDL, and VLDL cholesterol concentrations, particle numbers and sizes will be assessed.
- IgG4 (Screening visit only)
- Urine dipstick (pH, specific gravity, protein, glucose, ketones, bilirubin, blood)

All subjects with laboratory tests containing clinically significant abnormal values are to be followed regularly until the values return to normal ranges; until a valid reason, other than test-article related AE, is identified; or until further follow-up is deemed medically unnecessary.

Urine based  $\beta$ -hCG pregnancy tests will be performed in female subjects of childbearing potential per protocol specified visits. Additionally, in accordance with local country or site requirements, additional urine pregnancy tests may be performed. If a urine pregnancy test is positive, a serum pregnancy test must be performed to confirm the result. If positive, the Sponsor must be notified and the subject will be followed as outlined in [Section 11.1.9](#) until pregnancy outcome.

## 12. STATISTICS

### 12.1. Analysis Populations

The following analysis populations will be used:

#### **Intent-to-Treat (ITT) Population**

All randomized subjects who receive any amount of investigational product will be included in the ITT population. Treatment assignment will be based on the randomized treatment. The ITT population will be used for the analysis of all efficacy data.

#### **Week 12 Completer Population**

Completer population will include all ITT subjects who complete the DB Week 12 ALP assessment. Treatment assignment will be based on the randomized treatment.

#### **Week 24 Completer Population**

Completer population will include all ITT subjects who complete the DB Week 24 ALP assessment. Treatment assignment will be based on the randomized treatment.

## Safety Population

The Safety population will include all subjects who receive any amount of investigational product. Treatment assignment will be based on the treatment actually received. The Safety population will be used for the analysis of all safety data.

### 12.2. Determination of Sample Size

A sample size of 25 subjects per treatment group, a total of 75 subjects, will provide at least 90% power to detect a treatment difference for change in ALP assuming 20% dropout and the mean absolute changes in ALP for OCA and placebo treatment groups are approximately -20% and -5%, respectively, with a pooled standard deviation of 16, based on a 2-sided independent 2-group t-test at an alpha level of 0.05.

### 12.3. Efficacy Analysis

One of the primary objectives of this proof of concept trial is to evaluate the efficacy of OCA in subjects with PSC. The primary population for efficacy analyses is the ITT population. Sensitivity analyses will be conducted using the Completer population.

#### 12.3.1. Primary Efficacy Analysis

The primary efficacy endpoint is the Week 24 change from Baseline in ALP. The primary efficacy analysis will compare the Week 24 change from Baseline in ALP between OCA 10 mg treatment group and placebo using an analysis of covariance (ANCOVA) model with fixed effects for treatment group and randomization strata, and Baseline as a covariate.

#### 12.3.2. Secondary Efficacy Analysis

Secondary efficacy analyses of hepatic biochemistry and function parameters (eg, ALT, AST, and GGT) will be summarized by treatment group using descriptive statistics at Baseline and at each scheduled post-Baseline visit. The change from Baseline will also be summarized. Baseline is defined as the mean of all available evaluations prior to treatment. Hepatic biochemistry and function parameters will be analyzed using the same ANCOVA model as specified for the primary efficacy analysis.

A hierarchical approach will be used for multiplicity adjustments. If the primary efficacy analysis is statistically significant ( $p < 0.05$ ), the following order will be used in the testing procedure to compare the change from Baseline in ALP between OCA and placebo:

- Week 12: OCA 5 mg treatment group (randomized to 5 mg for the initial 12 weeks followed by 10 mg for the latter 12 weeks) vs. placebo
- Week 24: OCA 3 mg treatment group (randomized to 1.5 mg for the initial 12 weeks followed by 3 mg for the latter 12 weeks) vs. placebo
- Week 12: OCA 1.5 mg treatment group (randomized to 1.5 mg for the initial 12 weeks followed by 3 mg for the latter 12 weeks) vs. placebo

If at any step a comparison above is not statistically significant, then all subsequent comparisons will be exploratory rather than confirmatory.

In addition, secondary efficacy analyses of ALP response rates, defined as ALP to  $<1.5x$  ULN, will compare OCA treatment groups and placebo at Week 12 and Week 24 using a Cochran-Mantel-Haenszel test stratified by the randomization stratification factor.

Hepatic stiffness measurements (based on TE) will be summarized by treatment group using descriptive statistics at Baseline and at each scheduled post-Baseline visit. The ELF score and its components (HA, P3NP, T1MP-1) and the other markers of fibrosis and/or inflammation will be summarized based on available data by treatment group using descriptive statistics at Baseline and at each scheduled post-Baseline visit. The change from Baseline will be analyzed using the same ANCOVA model as specified for the primary efficacy analysis.

Subgroup analyses will be evaluated as deemed appropriate, including but not limited to, those subjects who start antibiotics after first dose of investigational product.

Full details regarding the planned analyses, methods, and outputs for the trial will be included in the SAP.

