### **Rationale for Primary Efficacy Endpoint**

The cholestatic conditions of PSC and PBC are both characterized by persistent increases in ALP. While UDCA did not show a treatment effect on clinical outcomes (Lindor 1997, Olsson 2005), follow up analyses showed that robust improvements in ALP, the achievement of normalized ALP levels or levels <1.5x ULN were associated with improved prognosis (Lindstrom 2013, Al Mamari 2013, Talwalkar 2013). Evaluation of OCA in PBC subjects has shown OCA to be associated with a clinically and statistically significant reduction in ALP. As such, this first trial of OCA in subjects with PSC will evaluate therapeutic response in terms of change from Baseline in ALP. Categorical improvements (ie, normalization or <1.5x ULN) will also be evaluated as secondary endpoints.

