##### **8.4.1. Stratification**

In order to ensure that factors which could potentially affect treatment response are randomized in equal proportions to the different treatment groups, subjects will be stratified by the following:

- The presence or absence of concomitant UDCA use, where no more than 50% of subjects recruited will be administering UDCA as part of standard of care at Day 0
- Total bilirubin level, where no more than 25% of subjects recruited will have a total bilirubin  $>1.5x$  ULN and  $<2.5x$  ULN at Screening

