8.3. Demographic and Baseline Characteristics

Demographic variables will include the following:

- Age at informed consent
- Age at informed consent categorized as <65 years and ≥ 65 years
- Sex
- Race/Ethnicity

Other Baseline characteristics will include the following:

- Weight (kg)
- Height (cm)
- BMI (kg/m^2)
- BMI categorized as $<30 \text{ kg}/\text{m}^2$ and $\geq 30 \text{ kg}/\text{m}^2$
- Hepatic ultrasound to assess bile duct patency performed (Yes/No)
- Key liver function test results as a continuous variable and categorized as follows by the ULN and the LLN unless otherwise specified:
 - ALP: $\leq 3 \times \text{ULN}$, $>3 \times \text{ULN}$; and, $\leq \text{median baseline ALP}$, $> \text{median baseline ALP}$

- Total Bilirubin: \leq ULN, $>$ ULN, $>$ ULN - \leq 1.5xULN, $>$ 1.5xULN - \leq 2xULN, $>$ 2xULN - \leq 2.5xULN
- International normalized ratio (INR): \leq 1.3, $>$ 1.3 stratified by subjects on/not on anticoagulants at the time of randomization

Arithmetic summary statistics as described in [Section 6.2.1](#) will be presented for age, weight, height, BMI, and key liver function test results. Frequency counts and percentages will be presented for age groups, sex, race/ethnicity, BMI category, key liver function categories, and hepatic ultrasound.

Race and ethnicity will be summarized as follows:

- Race
 - American Indian or Alaska Native
 - Asian
 - Black or African American
 - Native Hawaiian or Other Pacific Islander
 - White
- Ethnicity
 - Hispanic or Latino
 - Not Hispanic or Latino
 - Not reported
 - Unknown

Demographic and Baseline characteristics will be summarized for the ITT, Safety, PK, W12C, and W24C populations. All demographic and Baseline characteristics will be presented in data listings. The subgroup tables will be generated for IBD, UC, and CD regardless of the total number of patients in each group. For the remaining subgroups, the tables will be generated as long as each subgroup contains at least 10% of the subjects in the overall population.

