9.2.1. ALP Responders

ALP response rates, defined as ALP to $<1.5 \times \text{ULN}$, will compare OCA treatment groups vs. placebo at Baseline and all DB post-baseline visits using a Cochran-Mantel-Haenszel test stratified by the randomization stratification factor. For this analysis, missing values will be imputed as described in [Section 3.2.1](#).

The proportion of responders will be summarized by treatment group and visit as described in [Section 6.2.2](#) for W24C, W12C, and ITT populations.

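### The ALP <1.5x ULN responder test is valid but leaves out baseline ALP, so it gives up a little power and some protection against chance imbalance

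*Protocol*

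**What the plan says.** Response is a fixed cut: ALP below 1.5x ULN. Protocol 12.3.2 compares the OCA groups with placebo "at Week 12 and Week 24 using a Cochran-Mantel-Haenszel test stratified by the randomization stratification factor". SAP 9.2.1 repeats the test, "using a Cochran-Mantel-Haenszel test stratified by the randomization stratification factor", and widens it to Baseline and every double-blind post-baseline visit. SAP 6.3.2 counts a missing response as non-response, and the sensitivity analyses it lists change only the handling of missing data.

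Protocol 8.4.1 names the strata: "The presence or absence of concomitant UDCA use, where no more than 50% of subjects recruited" may be taking it, and "Total bilirubin level, where no more than 25% of subjects recruited" may lie between 1.5x and 2.5x ULN. ALP is not a stratum. Inclusion criterion 4 requires Screening ALP of at least 2x ULN and sets no upper limit.

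Elsewhere the plan does use baseline ALP. It is a covariate in the ANCOVA for change in ALP (Protocol 12.3.1, SAP 6.2.3 and 9.1). SAP 8.3 summarises "Key liver function test results as a continuous variable and categorized as follows by the ULN", with ALP split at 3x ULN and at the median, for description only. It is not among the subgroups in SAP 6.2.8.

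On the meaning of the cut, Protocol 4.6.1 says that robust improvement in ALP, "the achievement of normalized ALP levels or levels <1.5x ULN were associated with improved prognosis". SAP 5.2.1 also summarises responders by percentage reduction, from 10% to 40%. SAP 6.2.7 applies no multiplicity adjustment outside the hierarchy for change in ALP.

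**The concern.** With a fixed cut and an open-ended entry range, two subjects on the same treatment with the same percentage fall can be classed differently only because they started at different levels. Baseline ALP is therefore a strong predictor of response, and the plan treats it as one in the primary analysis of the same biomarker. A responder test that ignores it has two weaknesses. It leaves explainable variation in the comparison, which costs power. And with 25 per arm, one arm may by chance hold more subjects close to 2x ULN; the planned test has no means of allowing for this once it has happened. The value needed to adjust is already collected.

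**Working it through.** **1. The plan's own power figure.** The only one is for change in ALP: 25 per arm, difference 15, SD 16, two-sided 0.05. Noncentrality = 15 / (16 × √(2/25)) = 3.31 on 48 df, giving 90.1%. This reproduces the stated 90% for 25 evaluable subjects per arm. The documents give no power for the responder test.

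**2. Dependence on baseline.** Required fall from b × ULN = 1 − 1.5/b. For illustration, take the Protocol's −20% and −5% with SD 16 as percentage changes, normally distributed. P(response) = Φ((−required fall in % − mean)/16).

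| Baseline | Required fall | P, OCA | P, placebo |
|---|---|---|---|
| 2x ULN | 25% | 37.7% | 10.6% |
| 2.5x | 40% | 10.6% | 1.4% |
| 3x | 50% | 3.0% | 0.25% |
| 4x | 62.5% | 0.4% | 0.02% |

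A placebo subject at 2x ULN has the same chance of response as an OCA subject at 2.5x.

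**3. Overall validity of the planned CMH.** Assumptions: 25 per arm, baseline = 2 + lognormal (median 2.5x ULN, log-SD 0.8), SD 16%, 48% on UDCA, 15% in the upper bilirubin band, 20% dropout as non-response, 15,000 null trials. Type I error was 3.9% when both arms change by −20% and 4.9% when both change by −30%.

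**4. Chance imbalance, same null simulation.** The arms differ by 20 points or more in the share at or below 2.5x ULN in about 19% of trials. When both arms change by −30%, the chance of a false OCA win (nominal 2.5%) is 5.7% if such an imbalance favours OCA and 0.5% if it favours placebo. When both change by −20%, the figures are 4.3% and 0.7%.

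**5. Power, residual test.** Regress response on log baseline ALP with arms pooled, then compare residuals within the four strata by mean-score CMH. Baseline = 2 + exponential, mean 0.8 or 1.5; placebo −5%; SD 16%; 20% dropout; 2,500 trials.

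| OCA mean | Mean 0.8: planned → adjusted | Mean 1.5: planned → adjusted |
|---|---|---|
| −20% | 14.7% → 14.6% | 4.6% → 6.5% |
| −30% | 60.5% → 61.5% | 33.9% → 36.4% |
| −40% | 93.2% → 94.5% | 79.6% → 82.2% |

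Across exponential and lognormal baselines the change was about −0.5 to +3 points, with size 4% to 5% for both tests. Without dropout, four scenarios gained 2.3 to 3.8 points (for example 70.4% → 73.3%). Dropout shrinks the gain because a missing subject is a non-responder whatever the baseline.

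**6. Power, logistic adjustment with re-randomisation.** Model: UDCA, bilirubin, log baseline ALP; mid-p; lognormal baseline; 20% dropout; 1,500 trials. The comparator is the strata-only statistic, also re-randomised.

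| OCA mean | Median 2.5x ULN | Median 3x ULN |
|---|---|---|
| −20% | 9.7% → 15.5% | 1.8% → 7.4% |
| −30% | 58.8% → 64.1% | 22.7% → 31.3% |
| −40% | 94.6% → 95.8% | 72.5% → 78.1% |

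Five of the six gains lie between 5.3 and 8.6 points; where power is already near 95% the gain is 1.2. In the one null case run, size was 4.3% without and 5.7% with adjustment (Monte Carlo SE √(0.05 × 0.95/1500) = 0.6 points), so part of the gain may be size. The planned asymptotic CMH in these scenarios had power 13.8%, 62.5% and 95.7% (median 2.5x) and 1.5%, 25.3% and 78.3% (median 3x). Against it, the adjusted test ranges from 0.2 points lower to 6.0 higher. These are separate runs, so a point or two is noise.

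**7. Forms that do not serve.** A plain asymptotic logistic score test ran at 5.5% to 6.1% under the null with dropout, and 6% to 7% without. Adding a median split on baseline ALP to the four strata lowered power (62.5% → 58.0% at median 2.5x, OCA −30%).

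**The case against.** The planned test is a standard, prespecified choice that controls its error rate, so this is a matter of efficiency. That stands.

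A reader might take the 5.7% in step 4 as an inflated false-positive rate. It is not. It applies only to the minority of trials with a large imbalance in one direction, and trials with the opposite imbalance offset it. The ordinary effect of imbalance is also small. In the simulations without dropout, the between-arm difference in the share above 3x ULN had SD 13 to 14 points, and each 10 points moved the responder difference by about 1 to 2.6 points. One SD therefore moves it by 1.3 to 3.6 points, against a sampling SE of about 10 points at 30% versus 5% (√(0.3 × 0.7/25 + 0.05 × 0.95/25) = 0.10).

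A reader might also take <1.5x ULN as the one endpoint the protocol ties to prognosis. Protocol 4.6.1 lists it beside robust improvement and normalisation, then makes change in ALP primary and the categories secondary.

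The percentage reading in step 2 is an assumption: SAP section 4 says the planning figures are absolute changes and the percent signs were left in by oversight. The required falls do not depend on that reading; the probabilities and simulated powers do.

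Finally, change and percentage change in ALP are analysed with baseline as covariate, and percentage-reduction responders depend less on the starting level. These limit the harm but do not adjust the responder comparison.

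**Conclusion.** The point holds as a cheap improvement of low severity. The responder test omits a strong predictor that the plan already collects and already uses in its primary model. The cost is modest power and exposure to chance baseline imbalance, not an inflated overall error rate. With 20% dropout as non-response, the residual test gains about 0 to 3 power points. Logistic adjustment with re-randomisation gains about 5 to 9 points like for like in some scenarios, and less against the CMH as planned.

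These sizes rest on assumed baseline distributions with a floor at 2x ULN, normal percentage changes and SD 16%; the documents give no baseline ALP distribution. At −20% versus −5%, power is poor with or without adjustment. A large power loss, or a threat to the trial's main conclusion, is not supported: the endpoint is secondary, outside the hierarchy, and in a proof-of-concept trial.

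**What to change.** Before the double-blind database lock, add to SAP 9.2.1 a responder comparison adjusted for baseline ALP:

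- Use log baseline ALP in multiples of ULN, as a continuous covariate.
- Regress response on it with arms pooled, and compare residuals within the UDCA × bilirubin strata by mean-score CMH or by re-randomisation. Name one of the two in advance.
- Do not use a plain asymptotic logistic score test or a median split.
- Keep missing as non-response, and report the planned CMH alongside.
- Give a baseline-standardised risk difference with 95% CI only if responder counts allow a stable estimate, with the condition written down beforehand. In the step 5 simulations with dropout, placebo had no responders in 59% to 73% of trials.

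Protocol 12.3.2 leaves analysis details to the SAP, so the change can be made there. It needs SAP wording and a few lines of code, and no new data. The downside is one extra modelling step and the care that small-sample inference requires.
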